#### Table 3. Results from power calculations

PREPARE | Multi-centre EuRopean study of MAjor Infectious Disease Syndromes

## 8.3 Power calculation

#### 8.3.1 Number of hospitalised subjects needed

Based on the demographic and clinical data from 9 large clinical studies (24–32) in patients hospitalized with ARI we can expect about 4.9% of ARI patients to be infected with Influenza A, 4.6% with RSV, 3.9% with HRV. If we include 1500 ARI patients we expect to find group sizes of at least 11 in all groups across the major pathogens and major comorbidity groups (as shown in figure 1). This power calculation is based on detecting individual differentially expressed genes, which requires more power than detecting differentially/up- or down regulated pathways or clusters of genes.

PATHOGENS	mean (range) %
Influenza A	4.9 (4.8-5.0)
RSV	4.6(2.0-7.2)
HRV	3.9 (3.9-3.9)
Streptococcus pneumoniae	6.9 (0.8-13.3)

 Table 4. Projected prevalence of pathogens in hospitalised ARI patients based on available literature

#### Table 5. Projected prevalence of comorbidities in hospitalised ARI patients based on available literature

COMORBIDITIES	mean (range) %
Chronic pulmonary disease	31.6 (19.4-42.0)
Chronic cardiovascular disease	20.9 (10.0-41.9)
Chronic metabolic disease	23.0 (14.0-40.9)
No comorbidity	35.8 (18.3-66.7)

#### 8.3.2 Number of primary care subjects needed

Based on the demographic and clinical data from the GRACE cohort (Genomics to combat Resistance against Antibiotics in Community-acquired LRTI in Europe, http://www.grace-lrti.org/) in primary care patients presenting with ARI, we can expect about 9.9% of patients with influenza A infection, 4.6% with RVS and 20.1% with HRV. We expect 50% (range 45-65%) of ARI patients in primary care not to have comorbidities. If we include 500 primary care patients we expect to find group sizes of at least 11 in patients without comorbidities infected with influenza virus A, HRV, RSV or *Streptococcus pneumoniae*.

# PATHOGENSGRACE data (%)Influenza A9.9RSV4.6HRV20.1Streptococcus pneumoniae5.5

Table 6. Prevalence of pathogens in GRACE cohort

# 8.4 Statistical considerations regarding outcome measures

#### 8.4.1 RNA expression profiles

#### Correction for Multiple Comparisons

To control for multiple testing and reduce the false positive rate (FDR), stringent statistical criteria will be used to identify nominal 2-fold differentially expressed genes (i.e. effect size of 1 in absolute terms on a base-two logarithmic scale) with raw P-value < 0.05 and Benjamini-Hochberg False Discovery Rate <0,05.

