# 3.4 Study Aims

#### 3.4.1 Determinants of ARI disease severity

The primary aim of this study is to identify host and pathogen related determinants of disease severity of ARI. In this study we will include a prospectively defined and sufficiently sized patient cohort that will allow investigations of relative contributions of host and pathogen factors in development of mild, moderate and severe ARI. The sample size of this study is determined to provide adequate power to identify differences in RNA expression profiles between groups of patients with ARI stratified into groups by major categories of comorbidity (chronic pulmonary/cardiovascular/metabolic disease), and

PREPARE | Multi-centre EuRopean study of MAjor Infectious Disease Syndromes

the major causative pathogens (Influenza A, HRV, RSV and *Streptococcus pneumoniae*). Setting a high bar with regards to sample size, by basing our power calculation on the ability to detect differentially expressed genes between these predefined groups, will ensure the groups will be large enough to also compare less complex determinants of ARI severity, e.g. local and systemic innate and adaptive immune markers, and pathogen markers (e.g. pathogen load).

Our analysis will identify differentially expressed genes between patients with different comorbidities within and across ARI aetiologies and severities by combining a fold change assessment (>2-fold nominal change expression levels) combined with a p<0.05 correcting for multiple comparisons using the Benjamini-Hochberg False Discovery Rate (FDR) < 0.05 in accordance with guidelines from the MicroArray Quality Control (MAQC) group (22).

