# 8.2 Estimation of minimally required group sizes

We assume that the expression of each gene is normally distributed on the log scale and that the variance is the same in the different groups and thus the only difference between the groups is the mean. At an alpha of 0.05 and at an expected standard deviation of the gene intensity measurements on the base-two logarithmic scale of 0.7 (realistic for genes that are expressed at moderate to high levels), we expect to be able to detect 90% of >2 fold differentially expressed genes (i.e. an absolute effect size of 1 on a base-two logarithmic scale) between groups of 11 patients. These estimations are likely to be on the conservative side as we chose to err on the side of caution with regard to the chosen value for standard deviation. The calculation was based on the Affymetrix HG U133plus2 microarray platform, which contains 54,515 probe-sets.

	effect size in fold change			
power	2	1.75	1.5	
60%	5	8	15	
70%	7	10	18	
80%	8	12	23	
90%	11	16	31	
95%	13	20	38	

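### Table 3 gives power for a p<0.05 test alone, but the hit rule also requires an observed 2-fold change, so a gene with a true change of exactly 2-fold is detected at most about 50% of the time, not 90%

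*Protocol*

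**What the plan says.** Section 8.2 sets out the sizing assumptions: "We assume that the expression of each gene is normally distributed on the log scale and that the variance is the same" across groups, with a "standard deviation of the gene intensity measurements on the base-two logarithmic scale of 0.7". It continues "At an alpha of 0.05 and at an expected standard deviation" and concludes that "we expect to be able to detect 90% of >2 fold differentially expressed genes", explained as "an absolute effect size of 1 on a base-two logarithmic scale", "between groups of 11 patients". Table 3 extends this to true changes of 1.75-fold and 1.5-fold, with 16 and 31 per group for 90% power. Nothing in 8.2 or Table 3 mentions a cut on the observed fold change.

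The decision rule is given elsewhere. Section 3.4.1 identifies genes by "combining a fold change assessment (>2-fold nominal change expression levels) combined with a p<0.05", with Benjamini-Hochberg FDR control at 0.05. Section 8.4.1 repeats this as "nominal 2-fold differentially expressed genes (i.e. effect size of 1 in absolute terms on a base-two logarithmic scale) with raw P-value < 0.05", again with FDR below 0.05. The primary outcome in the synopsis and in section 5 carries the same requirement of at least a 2-fold difference.

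The group size of 11 feeds the enrolment calculations in 8.3.1 and 8.3.2. Section 8.1.2 and the legend to Figure 1 then claim power of 90% or more across the predefined subgroups.

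**The concern.** The cut-off on the observed change is set at the same value as the true effect used for power. An unbiased estimate of a true log2 difference of 1 falls below 1 half the time, so a gene sitting at the design effect fails the fold-change condition half the time, however convincing its p-value. The power calculation leaves this condition out, so the 90% belongs to a different rule from the one that will produce the gene lists.

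The figure matters because it supports the group sizes and the general claims of adequate power for the primary outcome. The study also intends to compare gene lists across pathogen and comorbidity strata. A reader who believes that 90% of genes at the design effect are found in each stratum will take a gene's absence from one list as evidence that it is specific to another stratum. Under the joint rule, absence is much weaker evidence than that.

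**Working it through.** **Inputs (all from 8.2).** SD 0.7 on the log2 scale, equal in both groups; normal distribution; alpha 0.05; 11 per group; true log2 difference 1. Sidedness is not stated; two-sided is assumed because it reproduces the table. The hit rule is from 3.4.1 and 8.4.1.

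**Step 1: reproduce Table 3.** Normal approximation, n per group = 2 × [0.7 × (1.960 + 1.282) / log2(fold)]²:

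| True fold | log2 | n for 90% | Table 3 |
|---|---|---|---|
| 2 | 1.000 | 10.3, so 11 | 11 |
| 1.75 | 0.807 | 15.8, so 16 | 16 |
| 1.5 | 0.585 | 30.1, so 31 | 31 |

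The other 12 cells match as well. The table is therefore power for the p-value criterion alone. With the exact two-sample t-test, power at 11 per group is 89.0%.

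**Step 2: which condition binds at n = 11.** SE = 0.7 × √(2/11) = 0.298. The t-test with 20 degrees of freedom needs an observed difference of about 2.086 × 0.298 = 0.62 log2 (1.54-fold). The fold-change cut needs 1.00. Before FDR, the cut is the binding condition.

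**Step 3: joint rule at a true 2-fold change.** The observed difference is normal with mean 1 and SE 0.298, so P(observed ≥ 1) = 0.50. A 2-fold change in the wrong direction is negligible. Simulation (1,000,000 genes per case, raw p<0.05):

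| n per group | p<0.05 alone | p<0.05 and observed ≥ 2-fold |
|---|---|---|
| 11 | 89% | 50% |
| 18 | 99% | 50% |
| 100 | 100% | 50% |

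**Step 4: larger true changes, n = 11, raw p<0.05.** The joint rule gives about 72% at 2.25-fold, 86% at 2.5-fold and 97% at 3-fold. The true change needed for 90% is 2^(1 + 1.282 × 0.298) = 2^1.38, about 2.6-fold.

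**Step 5: the other columns of Table 3, in the 90% row.**
- 1.75-fold, n = 16: SE 0.247, z = (1 − 0.807)/0.247 = 0.78, so about 22%.
- 1.5-fold, n = 31: SE 0.178, z = (1 − 0.585)/0.178 = 2.33, so about 1%.

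Below 2-fold, adding patients lowers the chance of passing the cut, because the estimate settles at a value under it.

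**Step 6: the FDR condition.** It can only reduce these figures. The per-gene threshold it implies depends on the data and is not given. As an illustration, with an assumed threshold of 0.001 at n = 11, joint detection at 2-fold is about 32%, and a true change of about 3-fold is needed for 90%. An observed difference of exactly 1 gives t = 1/0.298 = 3.35, p about 0.003. If the effective threshold falls below that, FDR rather than the fold cut becomes the binding condition for a gene with average variance.

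**The case against.** The strongest reply is that 8.2 promises detection of genes changing by more than 2-fold, and exactly 2-fold is the lower edge of that class. This stands as a limit on the point. Genes above the edge do better and improve with sample size: at a true 2.25-fold change the joint rule gives 72% at n = 11 and 96% at n = 100. Averaged over the class, the rate depends on how true effects are distributed, which the protocol does not say. If the excess over 1 log2 unit is assumed exponential, the average at n = 11 before FDR runs from 62% (mean excess 0.1) to 90% (mean excess 1.0). A reader might infer that the stated 90% is really at most 50% at any sample size. The documents support that only for genes at exactly 2-fold. The reply does not rescue Table 3, however, because its calculation is made at exactly that effect.

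It could also be said that the word nominal merely names the target effect. Section 3.4.1 does not allow that reading, since it describes a fold-change assessment combined with the p-value.

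Eleven is a minimum, and planned enrolment (2,250 and 750) exceeds the 1,500 and 500 used in 8.3. That helps genes above 2-fold but not those at 2-fold.

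Finally, a reader might infer that two strata with the same true 2-fold change would both list a gene a quarter of the time (0.5 × 0.5). That needs exactly 2-fold in both strata and independent estimates; contrasts that share a comparison group are correlated. It is not a general figure for this study.

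**Conclusion.** The point holds at the effect the protocol powers for. The 90% in 8.2 and Table 3 is correct to within rounding for a p<0.05 test, but it is not the power of the stated hit rule. The 50% rests on the protocol's own SD, normality and equal-variance assumptions, on a two-sided test, and on reading the nominal 2-fold change as an observed quantity.

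Both the 50% and the 2.6-fold figure are upper bounds on performance, since they leave out FDR. They should not be read as the power of the full rule. Nor do the documents show that the enrolment target is wrong or that the study cannot find strongly changed genes: at 11 per group and before FDR, a true 3-fold change is detected about 97% of the time. What is wrong as written is the match between the power statement and the decision rule.

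**What to change.** Restate 8.2 and Table 3 as power for the joint rule, meaning an observed change of at least 2-fold together with the p-value and FDR criteria. Say that detection is at most 50% at a true 2-fold change, and that 90% is reached only for true changes of at least about 2.6-fold at 11 per group. Mark these as best-case figures before FDR, and give one or more assumed per-gene thresholds so that the reader can see the reduction. Remove the 1.75-fold and 1.5-fold columns, or label them as power for the p-value test alone. Limit the 90% claims in 8.1.2 and the Figure 1 legend accordingly.

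The cost is a recomputed table and a few sentences; enrolment, sampling and the analysis rule are unchanged.

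The sponsor could instead drop the observed 2-fold cut, call genes on the FDR-controlled test, and report fold changes with intervals. That is a larger step. It would alter the primary outcome definition in the synopsis and section 5 and the rule in 3.4.1, and it would lengthen the gene lists with changes below 2-fold. The power figure under FDR would still have to be computed.

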#### Dimension reduction

Dimension reduction analysis of expression levels aims at identifying genes that vary the most amongst subjects and phenotypic classes, using methods such as Principal Component Analysis or Multi-Dimensional Scaling.

#### Class Discovery

Class discovery, or unsupervised cluster analysis aims at grouping genes or samples or both, using solely measures of similarity of expression levels, using methods such as hierarchical clustering, K-means clustering and bi-clustering in combination with resampling and bootstrapping.

#### Supervised Classification Methods

Supervised classification methods use information on existing, labelled classes to build a classifier, using methods such as linear discriminant analysis. Some methods combine class discovery and classification (33).

#### Multiple testing

Correction with multiple testing will rely on the False Discovery Rate method (34). Analyses will be performed using standard packages in R, version 3.1 (35).

#### Gene regulatory networks

A major task in transcriptome analysis is to derive the interaction between genes from the expression levels measured. Relations between genes are represented as a network representing genes as nodes and interactions as edges. Inference of such network is an active field of research and numerous methods exist and are being developed. Analysis of these networks allows the identification of highly connected genes and novel interactions (36–38).

#### 8.4.2 Pathway and network analysis

#### Functional Annotation and Pathway Enrichment analysis

One approach for functional grouping of genes identified as relevant from a statistical viewpoint is realized by utilizing gene ontologies (GO (39)). Statistical tools exist to identify enriched or depleted categories for a list of genes or proteins of interest. We will use Database for Annotation, Visualization, and Integrated Discovery (40) (DAVID) or BiNGO(41), and pathway databases like KEGG (42) and Reactome (43) to complement the functional ontologies.

#### Gene Set Enrichment Analysis

This type of analysis ignores what we already know about the biology of a system, and identifies enriched terms without regard for how they are related to one another. Gene Set Enrichment Analysis operates over the whole of the data from a microarray experiment, so no data points are lost prior to functional analysis. It also makes uses of prior knowledge to group sets of genes by related function, meaning that over-representation of a group of functions is considered, as opposed to isolated individual functions. The most commonly used tool for Gene Set Enrichment Analysis is GSEA (44).

PREPARE | Multi-centre EuRopean study of MAjor Infectious Disease Syndromes

24

#### Network clustering and correlation network

Each gene is a node and each edge indicates co-expression of two genes under the conditions of the experiment. The use of correlation networks for gene expression data is supported by Cytoscape (45) using either the MCODE (46) or ClusterMaker (47) plugin.

#### 8.5 Statistical analysis of secondary outcome measures

Statistical analysis of secondary endpoints will be descriptive in nature and include estimates of rates and proportions. Hypothesis testing is not envisaged to be a part of the statistical analysis of secondary endpoints.

All participants with evaluable samples and informed consent will be included in the analysis.

Proportions will be estimated for the prevalence of each pathogen in respiratory tract samples; the proportion of cases receiving antibiotics, antivirals, antifungals and/or immunomodulators; and proportion not surviving to 28 days post enrolment. Estimates will be presented for primary and hospital care groups separately, with 95% confidence intervals estimated using the binomial exact method. Additional binary endpoints will be analysed in the same manner.

Time to event variables such as time to discharge (length of stay) or time on ventilation will be described using the Kaplan-Meier method.

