# 7.2 Recruitment and informed consent

The participant must sign and date the latest approved version of the Informed Consent form before any study specific procedures are performed.

Written and verbal versions of the Participant Information Sheet and Informed Consent will detail the exact nature of the study; the implications and constraints of the protocol; and any risks involved in taking part. It will be clearly stated that the participant is free to withdraw from the study at any time for any reason without prejudice to future care, and with no obligation to give the reason for withdrawal. Participant Information Sheets will be available in the common local language.

Written Informed Consent will be confirmed by the dated signatures of the participant and by the person who presented and obtained the informed consent. The person obtaining consent must be suitably qualified and experienced, and be authorised to do so by the Principal Investigator. A copy of the signed Informed Consent will be given to the participants. The original signed form will be retained at the study site.

PREPARE | Multi-centre EuRopean study of MAjor Infectious Disease Syndromes

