#### 7.2.2.1 Study consenting procedures during the SARS-CoV-2 pandemic

During the SARS-CoV-2 / COVID-19 pandemic, study procedures are adjusted to minimalize interference with clinical care and reduce the burden on the patient, especially with regard to shortages of personal protection materials. The following adjustments will be applied:

Patients who are eligible for the study will be approached by a member of their healthcare team. Verbal information on the study will be provided. If the patient gives verbal informed consent to participate in the study, the study procedures will be executed. Verbal informed consent will be recorded in the patient notes. Once the patient is deemed non-infectious, a member of the healthcare team will undertake the informed consent procedure as stated in section 7.2.2.

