# 11.7 Other ethical considerations

This observational study will not exclude pregnant women or older participants. We are aiming to include as broad a range of samples as possible to be representative of the general population.

It is expected that 2-5% of hospitalised participants might lose capacity at some point during the study. Should this occur, these participants would not be withdrawn from the study. In the UK, and other countries with similar ethical requirements, participants will be asked for their prior consent to continue the collection of study data and samples should they later lose capacity. This will be explained fully during the consent process and consent for use of data and samples will be reconfirmed verbally when/if they regain capacity. The prior consent is optional so participants may opt-out and would be withdrawn from the study should they become incapacitated. Proxy assent will also be sought in order to continue collecting study samples on participants who have lost capacity.

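### Section 8.5 makes mortality, ICU, ventilation and treatment proportions depend on an evaluable sample, and does not say whether pandemic verbal consent counts

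*Protocol*

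**What the plan says.** Section 8.5 defines the set once, before it lists any outcome: "All participants with evaluable samples and informed consent will be included in the analysis". The same section then applies proportions to pathogen prevalence, to treatment received and to the "proportion not surviving to 28 days post enrolment", "with 95% confidence intervals estimated using the binomial exact method". It adds: "Additional binary endpoints will be analysed in the same manner". From the outcome table in section 5, that brings in hospitalisation of primary care patients, in-hospital mortality, ICU/HCU admission, oxygen, ventilation and extra-corporeal support. Durations are covered too: "Time to event variables such as time to discharge (length of stay) or time on ventilation will be described using the Kaplan-Meier method". No other section names a population for these outcomes.

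On consent, the general rule in section 7.2 is: "The participant must sign and date the latest approved version of the Informed Consent form before any study specific procedures are performed". Section 7.2.2.1, which sits under secondary care and was added for the SARS-CoV-2 pandemic, starts study procedures on verbal informed consent recorded in the notes and then says: "Once the patient is deemed non-infectious, a member of the healthcare team will undertake the informed consent procedure as stated in section 7.2.2".

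Two other sections bear on who stays in. Section 7.3 keeps data collected before a withdrawal of consent unless the patient objects. Section 11.7 keeps participants who lose capacity, with an exception: "The prior consent is optional so participants may opt-out and would be withdrawn from the study should they become incapacitated".

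**The concern.** There are two separate faults.

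- **Sample condition.** Whether a patient died, was ventilated or received antibiotics is known from the clinical record. Requiring an evaluable research sample as well removes people for a reason that is not part of the outcome. If having a usable sample is related to severity, the proportions shift. This applies to both care groups and to the whole study period.
- **Consent condition.** For pandemic hospital patients there are two consent steps, and the second comes only when the patient is no longer infectious. If consent in 8.5 means the completed written procedure, a patient must survive, with capacity, to that point in order to be counted. Inclusion would then depend on the outcome being estimated.

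At stake are the descriptive mortality and severity estimates for the hospital group, which form a stated secondary objective.

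**Working it through.** The plan gives no figure to reproduce here: it states neither an expected mortality nor an expected share of missing samples or incomplete consent. The check is a reading of the text followed by an illustration on assumed rates.

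**Reading the text**

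1. Section 8.5 attaches the sample condition to all secondary outcomes. It does not confine it to pathogen prevalence, the listed outcome that does need a sample.
2. Section 7.2 ties dated signatures to written informed consent and requires a signed form before any procedure. Section 7.2.2.1 allows procedures without a signature and calls the first step verbal informed consent. Section 8.5 says informed consent without qualification. The exclusion criterion for absent consent in section 6.5 does not specify the form either.
3. No section covers death between the two steps. Section 7.3 deals with patients who withdraw. Section 11.7 relies on a prior consent explained during the consent process, which 7.2.2.1 defers.

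**Sample condition alone.** Let p be true mortality, f the share of deaths excluded and g the share of survivors excluded. Then

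reported mortality = p(1 − f) / [p(1 − f) + (1 − p)(1 − g)].

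Assume p = 10%.

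- No deaths and 5% to 20% of survivors lack a sample: 0.10/(0.10 + 0.90 × 0.95) = 10.5%, up to 0.10/(0.10 + 0.90 × 0.80) = 12.2%.
- 5% to 20% of deaths and no survivors lack a sample: 0.095/0.995 = 9.5%, down to 0.08/0.98 = 8.2%.

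So the direction is open. Day 0 samples are due within 24 hours of admission (Table 1b), so many early deaths would have one.

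**Consent condition, written reading, pandemic enrolees only.** With no survivors lost (g = 0) the formula becomes p(1 − f)/(1 − pf):

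| Assumed true mortality | 10% of deaths lost | 25% lost | 50% lost |
|---|---|---|---|
| 5% | 4.5% | 3.8% | 2.6% |
| 10% | 9.1% | 7.7% | 5.3% |
| 20% | 18.4% | 15.8% | 11.1% |

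For 10% mortality and 25% of deaths lost: 0.075/0.975 = 7.7%.

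**If survivors are lost too**, at p = 10% and f = 25%:

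- g = 10%: 0.075/(0.075 + 0.81) = 8.5%
- g = 25%: 0.075/(0.075 + 0.675) = 10.0%
- g = 40%: 0.075/(0.075 + 0.54) = 12.2%

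The downward shift disappears when the two losses are equal and reverses beyond that.

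**Against sampling error and dilution.** Take an assumed pandemic subset of 300 with 30 deaths, 8 of them lost. The estimate is 22/292 = 7.5%, exact 95% interval 4.8% to 11.2%, which still contains 10%. If the same 8 deaths are lost from a hospital group of 2,250 with 225 deaths, the group figure is 217/2,242 = 9.7%. If a quarter of deaths were lost across all 2,250 (56 of 225), it would be 169/2,194 = 7.7%, interval 6.6% to 8.9%, which excludes 10%. That last case needs every hospital participant to have enrolled under the pandemic procedure, although that procedure entered only with version 5.0 in April 2020 (Document History).

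**The case against.** The strongest reply concerns consent. Section 7.2.2.1 is the specific rule for the pandemic, uses the term verbal informed consent, has it documented and lets procedures begin on it. On plain wording such a patient has given informed consent and meets 8.5, so no death is lost. This is a fair reading and may be the intended one. What stands against it is that 7.2 still demands a signature first, with no exception, and nothing says what happens when the deferred step never takes place. The denominator should not depend on which reading an analyst adopts.

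A second reply is that 8.5 says who will be included and does not say that others are excluded. But it is the only population statement for these outcomes, so it works as their definition. A third is that endpoint-specific sets are often left to the SAP. That would hold if the protocol were silent, but it states a rule, and the rule does not fit the clinical outcomes.

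Three stronger conclusions are tempting, and the protocol does not support them.

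- **That mortality is certainly biased downward.** This needs the written-consent reading and deaths lost at a higher rate than survivors. The sample condition can push the other way.
- **That 45 to 113 hospital participants would be excluded.** This comes from the 2% to 5% expected to lose capacity in section 11.7, applied to 2,250. It counts all capacity losses. Section 11.7 retains them except those who opted out, for whom no rate is given, and 7.3 keeps data from before a withdrawal.
- **That the primary transcriptome comparison is thinned in the same way.** Section 8.5 concerns secondary outcomes and section 8.4 states no such set. The primary strata are influenza, rhinovirus, RSV and *Streptococcus pneumoniae*, so patients with SARS-CoV-2 alone fall outside them.

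**Conclusion.** The point holds in two parts of different strength. The sample condition in 8.5 is wrongly placed for mortality, ICU/HCU admission, ventilation and treatment outcomes; this follows from the text alone, and the bias it may cause has no fixed direction. The consent condition is ambiguous: sections 7.2 and 7.2.2.1 conflict, and 8.5 does not choose between them. Only if 8.5 means written consent can pandemic hospital patients who die or lose capacity before the deferred step leave the denominator, and only then, with survivors lost at a lower rate than deaths, is mortality lowered.

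The size cannot be derived from the protocol. The fall from 10% to 7.7% is an illustration within pandemic enrolees. It assumes the mortality, assumes that 25% of deaths are lost and assumes that no survivors are lost. In the hospital group as a whole it would be diluted by an unknown amount. The outcomes are descriptive, with no hypothesis tests, so the consequence is possible distortion of reported proportions. The wording should be corrected.

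**What to change.** - In 8.5, apply the evaluable-sample condition only to pathogen and laboratory outcomes.
- In 8.5, analyse clinical outcomes in all enrolled participants with recorded consent, whether written or verbal under 7.2.2.1, subject to ethics agreement and to the withdrawal rule in 7.3.
- Reconcile 7.2, 7.2.2.1 and 8.5: add the pandemic exception to the signed-form rule, and state how participants who die or lose capacity before the deferred step are handled.
- Report the number excluded from each analysis and the reason, with vital status where it is known and may be used.

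The cost is a change of wording and an ethics notification. No new data are needed. Denominators will differ slightly between secondary outcomes, so each table should state its own.
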